#### 8.11.2.4. Visit 4 – 2-Week Follow-up Visit (12 to 16 Days After Visit 2)

- Record AEs as described in Section 8.3.
- Review the participant's reactogenicity e-diary data. Collect stop dates of any reactogenicity e-diary events ongoing on the last day that the reactogenicity e-diary was completed and record stop dates in the CRF if required.
- Record nonstudy vaccinations as described in Section 6.5.
- Confirm details of any of the prohibited medications specified in Section 6.5.1 received by the participant if required for his or her clinical care.

- Discuss contraceptive use as described in Section 10.4.
- Collect a blood sample (approximately 25 mL) for immunogenicity testing.
- Ask the participant to contact the site staff or investigator if a medically attended event (eg, doctor's visit, emergency room visit) or hospitalization occurs.
- Ask the participant to contact the site staff or investigator (this could be via the COVID-19 illness e-diary) immediately if he or she experiences any symptoms as detailed in Section 8.13.
- Schedule an appointment for the participant to return for the next study visit.
- Complete the source documents.
- The investigator or an authorized designee completes the CRFs.

#### 8.11.2.5. Visit 5 – 1-Month Follow-up Visit (28 to 35 Days After Visit 2)

- Record AEs as described in Section 8.3.
- Record nonstudy vaccinations as described in Section 6.5.
- Confirm details of any of the prohibited medications specified in Section 6.5.1 received by the participant if required for his or her clinical care.
- Discuss contraceptive use as described in Section 10.4.
- Collect a blood sample (approximately 25 mL) for immunogenicity testing.
- Ask the participant to contact the site staff or investigator if a medically attended event (eg, doctor's visit, emergency room visit) or hospitalization occurs.
- Ask the participant to contact the site staff or investigator (this could be via the COVID-19 illness e-diary) immediately if he or she experiences any symptoms as detailed in Section 8.13.
- Schedule an appointment for the participant to return for the next study visit.
- Complete the source documents.
- The investigator or an authorized designee completes the CRFs.

#### 8.11.2.6. Between Visits 5 and 6

All participants will be contacted by the site and unblinded to study intervention allocation to allow placebo recipients the opportunity to receive BNT162b2 as part of the study. If the participant originally received placebo and wants to receive BNT162b2, he or she will follow the procedures in Section 8.16 and the SoA in Section 1.3.3.

# 8.11.2.7. Visit 6 – 6-Month Follow-up Visit (154 to 168 Days After Visit 2): Only for Those Participants Who Originally Received BNT162b2 or Placebo Recipients Who Decline BNT162b2

- Record SAEs as described in Section 8.3.
- Record nonstudy vaccinations as described in Section 6.5.
- Confirm details of any of the prohibited medications specified in Section 6.5.1 received by the participant if required for his or her clinical care.
- Collect a blood sample (approximately 25 mL) for immunogenicity testing.
- Ask the participant to contact the site staff or investigator if a medically attended event (eg, doctor's visit, emergency room visit) or hospitalization occurs.
- Ask the participant to contact the site staff or investigator (this could be via the COVID-19 illness e-diary) immediately if he or she experiences any symptoms as detailed in Section 8.13.
- Schedule an appointment for the participant to return for the next study visit.
- Complete the source documents.
- The investigator or an authorized designee completes the CRFs.
- Record any AEs that occur within the 48 hours after the blood draw as described in Section 8.3.

# 8.11.2.8. Visit 7 – 12-Month Follow-up Visit (350 to 378 Days After Visit 2): Only for Those Participants Who Originally Received BNT162b2 or Placebo Recipients Who Decline BNT162b2

- Record SAEs as described in Section 8.3.
- Collect a blood sample (approximately 25 mL) for immunogenicity testing.
- Confirm details of any of the prohibited medications specified in Section 6.5.1 received by the participant if required for his or her clinical care.

- Collect the participant's e-diary or assist the participant to remove the study application from his or her own personal device.
- Complete the source documents.
- The investigator or an authorized designee completes the CRFs.
- Record any AEs that occur within the 48 hours after the blood draw as described in Section 8.3.

#### 8.12. Unscheduled Visit for a Grade 3 or Suspected Grade 4 Reaction

If a Grade 3 local reaction (Section 8.2.2.2), systemic event (Section 8.2.2.3), or fever (Section 8.2.2.4) is reported in the reactogenicity e-diary, a telephone contact should occur to ascertain further details and determine whether a site visit is clinically indicated. If a suspected Grade 4 local reaction (Section 8.2.2.2), systemic event (Section 8.2.2.3), or fever (Section 8.2.2.4) is reported in the reactogenicity e-diary, a telephone contact or site visit should occur to confirm whether the event meets the criteria for Grade 4.

A site visit must be scheduled as soon as possible to assess the participant unless any of the following is true:

- The participant is unable to attend the unscheduled visit.
- The local reaction/systemic event is no longer present at the time of the telephone contact.
- The participant recorded an incorrect value in the reactogenicity e-diary (confirmation of a reactogenicity e-diary data entry error).
- The PI or authorized designee determined it was not needed.

This telephone contact will be recorded in the participant's source documentation and the CRF.

If the participant is unable to attend the unscheduled visit, or the PI or authorized designee determined it was not needed, any ongoing local reactions/systemic events must be assessed at the next study visit.

During the unscheduled visit, the reactions/events should be assessed by the investigator or a medically qualified member of the study staff such as a study physician or a study nurse, as applicable to the investigator's local practice, who will:

- Measure body temperature (°C) (axillary).
- Measure minimum and maximum diameters of redness (if present).

- Measure minimum and maximum diameters of swelling (if present).
- Assess injection site pain (if present) in accordance with the grades provided in Section 8.2.2.2.
- Assess systemic events (if present) in accordance with the grades provided in Section 8.2.2.3.
- Assess for other findings associated with the reaction and record on the AE page of the CRF, if appropriate.

The investigator or an authorized designee will complete the unscheduled visit assessment page of the CRF.

#### 8.13. COVID-19 Disease Surveillance

If a participant experiences any of the following, he or she is instructed to contact the site immediately and, if confirmed, participate in a telehealth visit as soon as possible, optimally within 3 days of symptom onset. During the 7 days following each vaccination, potential COVID-19 symptoms that overlap with solicited systemic events (ie, fever, chills, new or increased muscle pain, diarrhea, vomiting) should not trigger a potential COVID-19 illness visit unless, in the investigator's opinion, the clinical picture is more indicative of a possible COVID-19 illness than vaccine reactogenicity. Participants may utilize a COVID-19 illness e-diary via an application (see Section 8.14) installed on a provisioned device or on the participant's own personal device to prompt him/her to report any symptoms. Note that this does not substitute for a participant's routine medical care. Therefore, participants should be encouraged to seek care, if appropriate, from their usual provider.

- A diagnosis of COVID-19;
- Fever;
- New or increased cough;
- New or increased shortness of breath;
- Chills;
- New or increased muscle pain;
- New loss of taste/smell;
- Sore throat;
- Diarrhea;
- Vomiting.

### 8.13.1. Potential COVID-19 Illness Visit (Optimally Within 3 Days After Potential COVID-19 Illness Onset)

This visit is expected to involve the sharing of healthcare information and services via telecommunication technologies (eg, audio, video, videoconferencing software) remotely, thus allowing the participant and investigator to communicate on aspects of clinical care.

As a participant's COVID-19 illness may evolve over time, several contacts may be required to obtain the following information:

- Record AEs, as appropriate as described in Section 8.3.
- Confirm details of any of the prohibited medications specified in Section 6.5.1 received by the participant if required for his or her clinical care.
- Collect local test results of COVID-19 and local diagnosis of COVID-19 as available.
- Complete the source documents.
- The investigator or an authorized designee completes the CRFs.

### 8.13.2. Potential COVID-19 Convalescent Visit (28 to 35 Days After Potential COVID-19 Illness Visit)

This visit is expected to involve the sharing of healthcare information and services via telecommunication technologies (eg, audio, video, videoconferencing software) remotely, thus allowing the participant and investigator to communicate on aspects of clinical care.

- Record AEs, as appropriate as described in Section 8.3.
- Confirm details of any of the prohibited medications specified in Section 6.5.1 received by the participant if required for his or her clinical care.
- Complete the source documents.
- The investigator or an authorized designee completes the CRFs.

#### 8.14. Communication and Use of Technology

In a study of this nature that requires illness events to be reported outside of scheduled study visits, it is vital that communication between the study site and the participant is maintained to ensure that endpoint events are not missed. This study will employ various methods, tailored to the individual participant, to ensure that communication is maintained and study information can be transmitted securely. Using appropriate technology, such as a study application, a communication pathway between the participant and the study site staff will be established. The participant may be able to utilize his or her own devices to access this technology, or use a device provided by the sponsor. Traditional methods of telephone communication will also be available. The technology solution may facilitate the following:

- Contact with the investigator, including the ability of the participant to report whether or not he or she has experienced symptoms that could represent a potential COVID-19 illness (COVID-19 illness e-diary; see Section 8.13).
- An alert in the event that the participant is hospitalized.
- Visit reminders.
- Messages of thanks and encouragement from the study team.
- A platform for recording local reactions and systemic events (reactogenicity e-diary) see Section 8.2.2.

If a participant is not actively completing either the reactogenicity or COVID-19 illness e-diary, the investigator or designee is required to contact the participant to ascertain why and also to obtain details of any missed events.

#### 8.15. SARS-CoV-2 NAAT Results From Vaccination 1 and Vaccination 2 Visits

Nasal (midturbinate) swabs for SARS-CoV-2 NAAT are obtained at Visits 1 and 4 (clinical laboratory subset) or Visits 1 and 2 (standard participants) to describe the immune responses elicited by a prophylactic BNT162b2 vaccine in participants with or without confirmed COVID-19 before Dose 2 and during the study (the secondary and exploratory objectives).

Research laboratory—generated positive results from the Vaccination 1 and Vaccination 2 visit swabs will be provided to the site once available, but this will not be in real time. The investigator must report the positive result to the community health center according to the local regulation in Japan.

Participants who have a positive SARS-CoV-2 NAAT result prior to the Vaccination 2 visit (Visit 2 for standard participants, Visit 4 for the clinical laboratory subset) should be handled as follows:

- Positive SARS-CoV-2 test with no symptoms, either at Visit 1 or any time between Visit 1 and the Vaccination 2 visit: A positive test in an asymptomatic participant does not meet exclusion criterion 5; therefore, Vaccination 2 should proceed as normal.
- Confirmed COVID-19 (ie, symptoms and positive SARS-CoV-2 test): This meets exclusion criterion 5; therefore, Vaccination 2 should not be given but the participant should remain in the study.

## 8.16. Procedures for Administration of BNT162b2 to Those Originally Assigned to Placebo After Approval of Protocol Amendment 3

All participants will be contacted by the site and unblinded to study intervention allocation to allow placebo recipients the opportunity to receive BNT162b2 as part of the study. Visit 101 could occur at the same time as the original Visit 8 for the clinical laboratory subset or

Visit 6 for the standard participants, if the participants originally received placebo and want to receive BNT162b2.

#### 8.16.1. Visit 101 – Vaccination 3 (After Protocol Amendment 3 is Approved by the IRB)

Before vaccination and before any study-related procedures are performed, voluntary, written, informed consent (via an ICD addendum) will be obtained from the participant. Each signature on the ICD addendum must be personally dated by the signatory. The investigator or his or her designee will also sign the ICD addendum. A copy of the signed and dated ICD addendum must be given to the participant.

- Confirm the participant originally received only placebo at Vaccinations 1 and 2. Secondary confirmation by another site staff member is required.
- Perform a urine pregnancy test on WOCBP as described in Section 8.2.4.
- Discuss contraceptive use as described in Section 10.4.
- Record nonstudy vaccinations as described in Section 6.5.
- Confirm details of any of the prohibited medications, specified in Section 6.5.1, received by the participant if required for his or her clinical care.
- Ensure and document that inclusion criteria 2, 3, and 4 are met and exclusion criteria 1, 3, 6, 7, 8, 9, 10, 12, 13, and 15 are not met. If, in the investigator's judgment, vaccination is in the best interests of the participant, vaccination may proceed, even if inclusion criteria are not met and exclusion criteria are met. Such exceptions should be recorded in the participant's source documents.
- Measure the participant's body temperature (axillary).
- Ensure that the participant meets none of the temporary delay criteria as described in Section 5.5.
- Record AEs as described in Section 8.3.
- Collect a blood sample (approximately 25 mL) for immunogenicity testing. If a sample for this purpose has already been collected in the previous 7 days (eg, per the procedures at Visit 8 for the clinical laboratory subset or Visit 6 for the standard participants), a second sample need not be collected.
- Obtain the participant's vaccine vial allocation using the IRT system.
- Site staff member(s) will dispense/administer 1 dose of BNT162b2 into the deltoid muscle of the preferably nondominant arm.

- Site staff must observe the participant for at least 30 minutes after BNT162b2 administration for any acute reactions. Record any acute reactions (including time of onset) in the participant's source documents and on the AE page of the CRF, and on an SAE form as applicable.
- Ask the participant to contact the site staff or investigator if a medically attended event (eg, doctor's visit, emergency room visit) or hospitalization occurs.
- Ask the participant to contact the site staff or investigator (this could be via the COVID-19 illness e-diary) immediately if the participant experiences any respiratory symptoms as detailed in Section 8.13.
- Schedule an appointment for the participant to return for the next study visit.
- Complete the source documents.
- The investigator or an authorized designee completes the CRFs and the dispenser/administrator updates the study intervention accountability records.

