# 8.2.3. Surveillance of Events That Could Represent Enhanced COVID-19 Disease

As this is a sponsor open-label study, the sponsor will conduct unblinded reviews of the data during the course of the study, including for the purpose of safety assessment.

Participants will be surveilled for potential COVID-19 illness from Visit 1 onwards (see Section 8.13).

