# 8.3.1. Time Period and Frequency for Collecting AE and SAE Information

The time period for actively eliciting and collecting AEs ("active collection period") for each participant begins from the time the participant provides informed consent, which is obtained before the participant's participation in the study (ie, before undergoing any study-related procedure and/or receiving study intervention), through and including Visit 7 for the clinical laboratory subset and Visit 5 for the standard participants. In addition, any AEs occurring up to 48 hours after each subsequent blood draw must be recorded on the CRF.

SAEs will be collected from the time the participant provides informed consent to approximately 12 months after Dose 2 of study intervention (Visit 9 for the clinical laboratory subset, Visit 7 for the standard participants).

Confirmed COVID-19 diagnosis (SARS-CoV-2 positive test) will be collected as an AESI from the time the participant provides informed consent until study completion (Visit 9 for the clinical laboratory subset, Visit 7 for standard participants) (see Section 8.3.8).

Additionally, for those participants who originally received placebo but go on to receive BNT162b2 at Vaccinations 3 and 4, AEs will be collected from the time the participant provides informed consent (for receipt of Vaccinations 3 and 4) through and including Visit 103. SAEs and confirmed COVID-19 diagnosis (SARS-CoV-2 positive test) will be collected from the time the participant provides informed consent (for receipt of Vaccinations 3 and 4) to approximately 6 months after Dose 2 of BNT162b2 (Visit 104).

Follow-up by the investigator continues throughout and after the active collection period and until the AE or SAE or its sequelae resolve or stabilize at a level acceptable to the investigator and Pfizer concurs with that assessment.

For participants who are screen failures, the active collection period ends when screen failure status is determined.

If the participant withdraws from the study and also withdraws consent for the collection of future information, the active collection period ends when consent is withdrawn.

If a participant definitively discontinues or temporarily discontinues study intervention because of an AE or SAE, the AE or SAE must be recorded on the CRF and the SAE reported using the Vaccine SAE Reporting Form.

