# 8.3.8. Adverse Events of Special Interest

This section provides information on AESIs that may be detected during the study:

• Confirmed COVID-19 diagnosis (positive SARS-CoV-2 test)

All AESIs must be reported as an AE or SAE following the procedures described in Sections 8.3.1 through 8.3.4. An AESI is to be recorded as an AE or SAE on the CRF. In addition, an AESI that is also an SAE must be reported using the Vaccine SAE Reporting Form.

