### 8.16.4. Visit 104 – 6-Months After Vaccination 4 Follow-up Telephone Contact (175 to 189 Days After Visit 102)

- Contact the participant by telephone but, if desired, may be conducted in person.
- Record SAEs as described in Section 8.3.
- Record nonstudy vaccinations as described in Section 6.5.
- Confirm details of any of the prohibited medications, specified in Section 6.5.1, received by the participant if required for his or her clinical care.
- Collect the participant's e-diary or assist the participant to remove the study application from his or her own personal device.
- Inform the participant that his or her study participation has completed.
- Complete the source documents.
- The investigator or an authorized designee completes the CRFs.

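### The contact instruction at crossover Visits 101 to 103 names respiratory symptoms, which conflicts with Protocol Section 8.13 and the original-schedule visits and may lower ascertainment of mild, non-respiratory COVID-19

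*Protocol*

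**What the plan says.** Protocol 8.13 sets the surveillance rule for everyone: "If a participant experiences any of the following, he or she is instructed to contact the site immediately". The list that follows has ten items: a diagnosis of COVID-19, fever, cough, shortness of breath, chills, muscle pain, loss of taste or smell, sore throat, diarrhea and vomiting. Nothing in it is marked as a respiratory subset, and crossover participants are not excepted. Section 8.2.3 is equally general: "Participants will be surveilled for potential COVID-19 illness from Visit 1 onwards".

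On the original schedule, the visits that carry a contact instruction run from screening or Visit 1 to the 6-month visit. They ask the participant to call "immediately if he or she experiences any symptoms as detailed in Section 8.13".

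On the crossover schedule, Visits 101, 102 and 103 carry the instruction, in identical words at each: the participant is to call "immediately if the participant experiences any respiratory symptoms as detailed in Section 8.13".

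Section 8.3.8 lists one AESI, confirmed COVID-19. Section 2.3.1 names disease enhancement as a potential risk, and Section 4.2 gives that risk as the reason for the additional COVID-19 surveillance.

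**The concern.** The visit sections are the checklists that sites work from. A site that follows 8.16 to the letter gives a crossover participant a narrower prompt than 8.13 requires, and narrower than the one the same person was given on the original schedule. The narrower prompt is also the most recent one.

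This group has few other scheduled ways to pick up a mild infection. Crossover participants complete no reactogenicity e-diary (8.2.2). Their schedule (1.3.3) has no nasal swab, and its single immunogenicity sample is at Visit 101, so no later N-binding antibody result would reveal a missed infection. The unplanned illness visit remains in the schedule, but it depends on the participant making contact. What is at stake is how completely the study records its only AESI in people newly vaccinated with BNT162b2. No hypothesis test is affected, because the study has none.

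**Working it through.** The plan states no figure to reproduce on this point. The check is a comparison of wording, a count and some arithmetic on visit windows.

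**Count of triggers (Protocol 8.13).** There are 10 items: 1 diagnosis and 9 symptoms. Both versions of the instruction say symptoms, so the diagnosis item is not lost through the word respiratory. The right base is 9.

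| Reading of respiratory | Symptoms kept | Symptoms dropped |
|---|---|---|
| Cough, shortness of breath | 2 of 9 | 7 of 9 |
| Plus sore throat | 3 of 9 | 6 of 9 |
| Plus loss of taste or smell | 4 of 9 | 5 of 9 |

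On every reading, fever, chills, muscle pain, diarrhea and vomiting drop out.

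**Effect of the 7-day limit.** Section 8.13 adds a limit for all participants: "During the 7 days following each vaccination, potential COVID-19 symptoms that overlap with solicited systemic events" should not lead to an illness visit unless the investigator thinks COVID-19 the likelier explanation. The overlapping symptoms are exactly the five above. The narrower wording therefore changes little inside those windows.

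**Time at issue.**
- Visit 102 is 19 to 23 days after Visit 101, and Visit 104 is 175 to 189 days after Visit 102. Total: 19 + 175 = 194 to 23 + 189 = 212 days.
- Two 7-day windows make 14 days: 14/212 = 6.6% to 14/194 = 7.2% of the period. The wording matters for the other 93% or so.
- Visit 103 is 28 to 35 days after Visit 102. The gap to Visit 104 is 175 − 35 = 140 to 189 − 28 = 161 days, with no scheduled contact. In that gap the instruction given at Visit 103 is the latest one the participant has heard.

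**People affected.** The placebo arm is planned at 40 (9.2), so at most 40 of up to 120 + 40 = 160 eventual BNT162b2 recipients (25%).

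**Illustration on assumed values only.** The documents give neither a COVID-19 attack rate *a* nor the fraction *c* of cases that the prompts would capture. With n = 40, the chance of recording at least one case is 1 − (1 − a·c)^40:

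| a (assumed) | c = 1 | c = 0.75 | c = 0.5 |
|---|---|---|---|
| 1% | 0.331 | 0.260 | 0.182 |
| 2% | 0.554 | 0.454 | 0.331 |
| 5% | 0.871 | 0.783 | 0.637 |

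For example, 1 − (1 − 0.02 × 0.75)^40 = 1 − 0.985^40 = 0.454. The table shows how the chance would move if capture fell. It does not estimate how far capture falls under this wording.

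**The case against.** The strongest reply is that the instruction does not stand alone, and most of this reply is right.

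- It points to Section 8.13, whose full list applies to any participant. A reader might infer that crossover participants are told to report respiratory symptoms and nothing else. The text contains no such exclusion, and the same people were given the unrestricted instruction on the original schedule up to the 1-month visit.
- A reader might infer that a diagnosis made elsewhere goes unreported. At all three visits, a separate bullet asks the participant to call after any medically attended event or hospitalization, which would cover most outside diagnoses and severe illness.
- AEs are asked about at Visits 102 and 103, and Section 8.3.1 extends collection beyond that: "SAEs and confirmed COVID-19 diagnosis (SARS-CoV-2 positive test) will be collected from the time the participant provides informed consent" for Vaccinations 3 and 4, up to Visit 104.
- The COVID-19 illness e-diary is optional, but Section 8.14 requires the site to contact anyone not actively completing it.
- A reader might also fault Visit 104, whose checklist says "Record SAEs as described in Section 8.3" and does not name COVID-19. The original 6- and 12-month visits use the same words, and 8.3.1, to which the crossover schedule's footnote refers, already requires confirmed COVID-19 to be collected to Visit 104. That is not a crossover defect.

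What remains is narrower. The prompt about medical care misses mild illness for which no care is sought. AE questioning is retrospective, whereas 8.13 wants immediate contact and an illness visit within about 3 days of onset. The general rule in 8.13 reaches the participant largely through what the site is told to say.

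**Conclusion.** The inconsistency is real and repeated in three sections. Taken literally, the crossover instruction prompts for 2 to 4 of the 9 listed symptoms. It may therefore lower or unbalance detection of mild COVID-19 without respiratory symptoms in up to 40 participants, mainly outside the two 7-day post-vaccination windows. This assumes that sites follow the checklist wording and that participants act on the latest instruction.

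Under-detection is a risk, not something the documents show, and its size cannot be derived from them. Nor do they support an inference that AESI counts will differ between the two BNT162b2 cohorts because of this wording. SAP 6.1.1.3.2 asks for AESIs to be listed, crossover AEs and SAEs are summarized separately (Protocol 9.4.2, SAP 6.4.5), and no comparison of COVID-19 between those cohorts is planned. The cohorts also differ in calendar time, blinding and length of follow-up. The point concerns completeness of safety ascertainment and is worth correcting because the correction is nearly free.

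**What to change.** Reconcile Protocol 8.16.1, 8.16.2 and 8.16.3 with 8.13 by giving the instruction in the words used at the other visits, that is, to call "immediately if he or she experiences any symptoms as detailed in Section 8.13". In practice this deletes one word in each of three sections. The 7-day limit in 8.13 continues to apply unchanged, and Visit 104 needs no edit on this account.

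The cost is a short protocol clarification and possibly a few more telehealth illness contacts. There is no change to sample size, visit schedule, blood volume or the SAP.
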